Appendix 5. Columbia–Suicide Severity Rating Scale

[figure not shown]
C-SSRS – Baseline/Screening Version

[figure not shown]
**COLUMBIA-SUICIDE SEVERITY
RATING SCALE
(C-SSRS)**

[figure not shown]
Baseline/Screening Version

[figure not shown]
Version 1/14/09

[figure not shown]

[figure not shown]

[figure not shown]
C-SSRS – Since Last Visit Version

[figure not shown]
**COLUMBIA-SUICIDE SEVERITY
RATING SCALE
(C-SSRS)**

[figure not shown]
Since Last Visit Version 1/14/09

[figure not shown]

[figure not shown]
Appendix 6. Prohibited Concomitant Medication List

[figure not shown]
- Aminoglycoside antibiotics
- Baclofen
- Benzodiazepines
- Botulinum toxin therapy of any serotype
- Cannabinoids
- Carisoprodol
- Chlormezanone
- Curariform drugs
- Dalfampridine
- Dantrolene
- Gabapentin for anti-spasticity indication
- Meprobamate
- Methocarbamol
- Neuroleptics such as tricyclic antidepressants and narcotics
- Orphenadrine
- Cyclobenzaprine
- Tizanidine
- Tolperisone

[figure not shown]
Appendix 7. Urinary Symptom Profile Questionnaire

[figure not shown]
Urinary Symptom Profile - USP[®]

[figure not shown]

[figure not shown]

[figure not shown]

Appendix 8. [REDACTED]

Appendix 9. Summary of Changes

2. LIST OF ABBREVIATIONS AND DEFINITION OF TERMS

Only abbreviations and terms relevant to the SAP are repeated herein. The reader is referred to the protocol for the complete and comprehensive list of abbreviations and definitions of terms for the study.

Abbreviation	Definition
ADaM	Analysis data Model
AE	Adverse event
AERT	Arbaclofen extended-release tablets
ANCOVA	Analysis of covariance
CDISC	Clinical Data Interchange Standards Consortium
CGIC	Clinical Global Impression of Change
CRF	Case report form
C-SSRS	Columbia–Suicide Severity Rating Scale
DSMB	Data Safety Monitoring Board
ECG	Electrocardiogram
eCRF	Electronic case report form
EDSS	Expanded Disability Status Scale
FDA	Food and Drug Administration
ICH	International Conference on Harmonization
IRB	Institutional Review Board
IRT	Interactive Response Technology (system)
ITT	Intent-to-treat (population)
LOCF	Last observation carried forward
LS Means	Least-squares means
mAS	Modified Ashworth Scale
MedDRA	Medical Dictionary for Regulatory Activities
mITT	Modified ITT (population)
MMRM	Mixed model for repeated measures
MS	Multiple Sclerosis
mWOCF	Modified worst observation carried forward
PGIC	Patient Global Impression of Change
PMM	Pattern-mixture model
PP	Per-protocol (population)
PT	Preferred term
REML	Restricted maximum likelihood
SAE	Serious adverse event
SAP	Statistical Analysis Plan
SD	Standard deviation
SDTM	Study Data Tabulation Model
SOC	System organ class
TEAE	Treatment-emergent adverse event
TNmAS-MAL	Total Numeric-transformed mAS score of the most affected limb
USP	Urinary Symptom Profile - USP [®] questionnaire
WHO	World Health Organization
WHO-DD	World Health Organization – Drug Dictionary

3. INTRODUCTION

3.1. Preface

This document presents a statistical analysis plan (SAP) for Osmotica Pharmaceutical's Protocol OS440-3004 (*A Randomized, Double-Blind, Placebo-Controlled, Parallel-Group Study to Investigate the Safety and Efficacy of Arbaclofen Extended-Release Tablets for the Treatment of Spasticity in Patients with Multiple Sclerosis*).

Reference materials for this statistical plan includes the protocol OS440-3004 (CLN.OS440-3004.PR.A01 Dated: 19 SEP 2017).

The SAP described hereafter is an *a priori* plan. The SAP will be finalized and approved prior to unblinding of any study data. Statistical programming may occur as study data accumulate in order to have analysis programs ready at the time the study finishes. In such an event, arbitrary treatment group assignments must be randomly linked to subjects, effectively rendering any output of programs meaningless.

For the reasons stated here the conduct of the study in the field is considered to be independent of any study outcome that might materialize upon enactment of the currently proposed statistical plan.

3.2. Purpose of Analyses

The purposes of the planned analyses described in this SAP are to assess the safety and efficacy of oral arbaclofen extended-release tablets (AERT) in MS patients with spasticity. Results from the analyses completed will be included in the final clinical study report for OS440-3004, and may also be utilized for regulatory submissions, manuscripts, or other clinical development activities.

Post-hoc exploratory analyses not identified in this SAP may be performed to further examine the study data. These analyses will be clearly identified, where appropriate, in the final clinical study report. Additional analyses not prospectively identified in this SAP may also be completed for publications, or regulatory or funding inquiries. These analyses, if performed, may not be reported in the clinical study report, but will be fully documented in the document containing the additional analyses.

3.3. Summary of Statistical Analysis Changes to the Protocol

The analyses described in this analysis plan are consistent with the analyses described in the study protocol.

4. STUDY OBJECTIVES AND ENDPOINTS

4.1. Study Objectives

4.1.1. Primary Objective

The primary objective of this study is to demonstrate the safety and efficacy of arbaclofen extended-release tablets (AERT) for treatment of spasticity in patients with MS.

4.2. Study Endpoints

4.2.1. Primary Endpoint

The co-primary efficacy endpoints include the following:

- Total Numeric-Transformed Modified Ashworth Score – Most Affected Limb (TNmAS-MAL)
- Clinical Global Impression of Change (CGIC)

4.2.2. Secondary Endpoints

Secondary endpoints include the following:

Safety and Tolerability:

- Adverse events
- Vital signs
- Clinical laboratory tests
- 12-lead electrocardiograms (ECGs)
- Urinary Symptom Profile - USP© questionnaire (USP)
- Columbia-Suicide Severity Rating Scale (C-SSRS)

Efficacy:

- Patient Global Impression of Change (PGIC)
- Expanded Disability Status Scale (EDSS)
- TNmAS – Total Limbs (TNmAS-TL)

5. STUDY METHODS

5.1. General Study Design and Plan

As background for the statistical methods presented below, this section provides an overview of the study design and plan of study execution. The protocol is the definitive reference for all matters discussed in what follows.

This is a multicenter, randomized, double-blind, placebo-controlled, parallel-group study to evaluate the safety and efficacy of oral AERT in MS patients with spasticity. Two doses of AERT, 40 mg and 80 mg, will be compared with placebo. The treatment groups will be randomized in a 1:1:1 ratio. There will be a 9-day titration period, then a 75-day maintenance period, followed by a 7-day taper period.

Eligible subjects will undergo an at least 14-day washout period for withdrawal of all medications used for anti-spasticity and/or muscle relaxation prior to randomization. A baseline clinical evaluation will be performed (Visit 2) to confirm eligibility for study randomization, and subjects will be assigned to 1 of 3 treatment arms: (1) AERT 40 mg; 2) AERT 80 mg; or 3) placebo. During the first 9 days of drug administration, doses will be titrated about every 3 days to a fixed-dose of either AERT 40 mg, AERT 80 mg, or placebo BID. Subjects will remain at that fixed-dose for 75 days. At the end of the maintenance period, the subject's dose will be tapered for an additional 7 days before the subject returns to the site for a final safety evaluation at Day 92 (Visit 6).

The study design schema is presented in Figure 1. The schedule for assessments is presented in Table 1.

Figure 1 Study Design Schema

[figure not shown]

Table 1 Schedule of Assessments

Procedure	Screening Visit 1 Days -21 to 0	Baseline Visit 2 Day 1 (±3 days)	Visit 3 Day 10 (±3 days)	Visit 4 Day 42 (±5 days)	Visit 5 Day 84 (±5 days)	Final or Early Termination Visit 6 Day 92 (±5 days)
Written informed consent	X					
Inclusion and exclusion criteria	X	X				
Review study discontinuation criteria		X	X	X	X	
Withdrawal anti-spasticity medication	X					
Assign enrollment number	X					
Randomization		X				
Demography	X					
Medical/surgical history	X					
Physical examination	X					
Height	X					
Weight	X					X
Vital signs1	X	X	X	X	X	X
Hematology/serum chemistry/urinalysis	X	X	X	X	X	X
Electrocardiogram	X					X
Pregnancy test2	X	X	X	X	X	X
Dispense study medication		X	X	X	X	
Collect unused study medication			X	X	X	X
C-SSRS	X	X	X	X	X	X
TNmAS-MAL3	X	X		X	X	X
EDSS	X	X				X
CGIC				X	X	X
PGIC						X
USP® questionnaire	X	X	X	X	X	X
Adverse event assessment		X	X	X	X	X
Concomitant medications/therapies	X	X	X	X	X	X

C-SSRS = Columbia–Suicide Severity Rating Scale; TNmAS-MAL = Total Numeric-transformed modified Ashworth Scale score of the most affected limb; EDSS = Expanded Disability Status Scale; CGIC = Clinical Global Impression of Change; PGIC = Patient Global Impression of Change; USP = Urinary Symptom Profile.

Table 1 - Footnotes:

1. Vital signs will be measured with the subject in a supine position and in a standing position 3 minute after the supine assessment is completed. Body temperature and respiratory rate will be measured only during the supine assessment.
2. Premenopausal women of childbearing potential must have a negative serum pregnancy test within 28 days before Visit 2 (Baseline). Urine pregnancy testing will be done at Visits 2 through 6.
3. The TNmAS-MAL assessment will be performed prior any scheduled lab draws and will always be done by the study evaluator (someone other than the investigator) who has been appropriately trained to perform and assess the TNmAS-MAL, and when possible all TNmAS-MAL assessments should be performed for a particular subject by the same study evaluator throughout the study. The most affected limb will be determined by the study evaluator.
4. Performed by the investigator or sub-investigator not functioning as the study evaluator for the particular subject.

5.2. Randomization and Blinding

Two doses of AERT, 40 mg (20 mg BID) and 80 mg (40 mg BID), will be compared with placebo. The treatment groups will be randomized in a 1:1:1 ratio. The randomization schedule will be stratified by geographic region: Eastern Europe, Central Europe, and North America.

[figure not shown]
After Screening procedures have been completed at Visit 1, authorized site personnel will acknowledge that the applicable subject met all the specified inclusion criteria and none of the exclusion criteria and an enrollment number will be sequentially assigned. After the Screening clinical laboratory test results and other clinical assessments have been completed at Visit 2 (Baseline), assignment to a treatment group will then follow a predetermined list of randomization numbers, with each successive number receiving 1 of the 3 treatments in random order. Authorized site personnel will use the Interactive Response Technology (IRT) system to assign a kit number that corresponds to the randomization schedule. The kit box with the assigned kit number will be dispensed to the subject.

The randomization code will be provided by the Sponsor.

5.3. Analysis Variables

Variables to be analyzed include demographics and baseline characteristics, safety variables (adverse events, clinical laboratory investigations, vital signs, ECGs, USP questionnaire, and C-SSRS), and efficacy variables (TNmAS-MAL, CGIC, PGIC, EDSS, and TNmAS-TL). See Section 8 of the protocol for further details on the efficacy variables. Derived variables from study endpoints are described with the sections describing the analyses for these endpoints.

6. SAMPLE SIZE

7. GENERAL CONSIDERATIONS

7.1. Analysis Populations

There will be five (5) analysis populations defined for this study.

7.1.1. Screened Population (SCREEN)

Subjects who provide informed consent will be members of the screening population. The screening population will include the total number of subjects who were considered for this study, regardless of participation.

7.1.2. Intent-to-Treat Population (ITT)

Includes all subjects who are randomized. Subjects included in the ITT population will be analyzed as randomized. The ITT population will be used for analyses of accountability, demographics, baseline characteristics, and efficacy.

7.1.3. Modified Intent-to-Treat Population (mITT)

Includes the ITT population minus any subjects with MS relapse. Subjects in the mITT population will be analyzed as randomized. This will be a secondary supporting population for the co-primary efficacy analyses.

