Baclofen has been in clinical use for more than 35 years and the benefits and risks are well characterized. It is approved for the treatment of spasticity due to MS and spinal cord injury and is a first-line pharmacotherapy as described in the MS Council for Clinical Practice Guidelines for treatment of spasticity in MS. However, the therapeutic potential of baclofen is limited because it is poorly tolerated by patients due to the side effects of sedation, drowsiness, and worsening of fatigue. Therefore, an unmet medical need exists for an effective, better tolerated oral treatment of spasticity.

Baclofen is a racemate (rac-baclofen) consisting of an equal mixture of two enantiomers: the l- or R-enantiomer (arbaclofen) and the d- or S-enantiomer.

Osmotica Pharmaceutical is currently developing arbaclofen extended-release tablets (AERT) for the treatment of spasticity in patients with MS. Arbaclofen is the active R-enantiomer of

baclofen and it has been postulated that the efficacy of baclofen is primarily due to the R-enantiomer. This clinical study aims to demonstrate the clinical efficacy and improved tolerability of AERT in patients with spasticity due to MS.

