9.7.2 Adverse Event Definitions

9.7.2.1 Adverse Events

An AE is any unfavorable and unintended sign, symptom, or disease that appears or worsens in a subject after the subject signs the ICF for a clinical study.

Examples of what may be considered an AE include any of the following:

- A new illness.
- An exacerbation of a sign or symptom of an underlying condition or of a concomitant illness unrelated to participation in the clinical study or an effect of the study drug or comparator drug.

No causal relationship with the study drug is implied by the use of the term "adverse event." An exacerbation of a pre-existing condition/illness is defined as a more frequent occurrence or as an increase in the severity of the pre-existing condition/illness during the study. Planned or elective surgical procedures for pre-existing conditions that have not worsened are not AEs. However, any complication that occurs during a planned or elective surgery is an AE. (If the event meets the criteria for a SAE, such as an extended hospitalization, it will be considered an SAE). Conditions leading to unplanned surgical procedures may also be AEs.

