12.4 Withdrawal of Subjects

Withdrawn subjects are those who do not complete all evaluations and procedures outlined in the protocol. A subject will be considered to have discontinued prematurely if he/she withdraws after being randomized and prior to completing Visit 6 (Final Visit). Subjects who discontinue taking study drug for any reason for greater than 5 consecutive days must also be withdrawn from the study. Subjects may be withdrawn from the study because of any of the following:

- **Adverse Event:** An AE that, in the opinion of the Investigator or Sponsor, suggests that continued participation in the study is not in the subject's best interest for safety reasons (also see [Section 10](#)). All AEs that are present when the subject withdraws from the study will be followed as described in [Section 9.7.4](#).
- **Medical Condition:** Any medical condition that, in the Investigator's judgment, would increase the risk or interfere with the evaluation of study objectives.
- **Lost to Follow-up:** As per the comprehensive lost to follow-up guidance document that will be submitted to the IRB/IEC with the clinical protocol.
- **Subject Request:** Subject requests for any reason to be withdrawn or withdraws his/her consent.
- **Protocol Deviation:** A subject may be withdrawn from the study at the discretion of the Investigator or Sponsor due to poor compliance with protocol requirements that may compromise the study results or subject safety.
- **Enrollment in Another Study:** Enrollment in other protocols involving research drugs, medical devices, or surgeries.
- **Other Anti-spasticity Treatment:** Starting any other pharmacological anti-spasticity treatment during the study.

- **Relapse:** Subjects who experience an acute MS exacerbation/relapse (symptoms including but not limited to visual disturbance, dizziness, tingling, or extreme fatigue lasting greater than 24 hours and occurring at least 30 days after a previous relapse) requiring immediate therapy or adjustment in disease-modifying medication dose (eg, oral or intravenous high-dose steroid therapy). Upon resolution of symptoms, the subject may choose to be assessed for entry into the subsequent open-label extension study (Study OS440-3005).

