7.3.2.2. Imputation Methods

Observed cases, without imputation, will be used for the majority of analyses. A modified worst observation carried forward (mWOCF) imputation method will be utilized in a sensitivity analysis for the co-primary efficacy endpoints. For mWOCF imputed data, subjects who withdraw from the trial early due to an AE will have their missing data imputed using WOCF; all other missing data will be imputed using the last observation carried forward (LOCF).

If the relationship of an AE is missing, it will be considered treatment-related. Missing AE severity will be coded as severe.

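### The supportive mITT analysis deletes whole subjects for any MS relapse after randomisation, discarding valid earlier scores and no longer comparing the groups as randomised

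*SAP*

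**What the plan says.** SAP 7.1.3, in line with Protocol 11.2, defines the mITT as follows: "Includes the ITT population minus any subjects with MS relapse". Its role is limited: "This will be a secondary supporting population for the co-primary efficacy analyses". SAP 9.1.3 repeats the co-primary models in this population as a sensitivity analysis. The primary analysis uses the ITT population, which "Includes all subjects who are randomized".

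The mITT text does not define relapse. Protocol 7.7 and 12.4 describe it by symptoms ("symptoms including but not limited to visual disturbance, dizziness, tingling, or extreme fatigue lasting greater than 24 hours"), add a minimum gap of 30 days from a previous relapse, and require that the event needs immediate therapy or a change in disease-modifying dose. Subjects meeting that description are withdrawn. The mITT wording carries neither the treatment condition nor any limit on when the relapse must occur.

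Both co-primary models use two visits only, Day 42 and Day 84 (Protocol 11.4.1, SAP 9.1.2).

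**The concern.** Membership of the mITT depends on something that happens after treatment starts. Removing subjects on such an event means the arms compared are no longer the arms that were randomised. If relapse, or the labelling of an event as relapse, differs by arm or goes with outcome, the contrast can shift for reasons unrelated to effect on spasticity.

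The deletion is also wasteful. A score recorded before a relapse began is not contaminated by it, yet the rule removes it. The MMRM accepts partial records, so the whole subject need not go in order to drop the affected scores.

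What is at stake is the value of this analysis as support. It is offered as evidence that the co-primary result is robust, and agreement or disagreement with the ITT result would be hard to interpret.

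**Working it through.** **1. Timeline.** Titration of 9 days plus maintenance of 75 days gives 9 + 75 = 84. The 7-day taper is therefore Days 85 to 91. A relapse in the taper normally follows both modelled visits.

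**2. What each rule does with scores taken before onset.**

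| Relapse onset | Valid earlier scores | ITT model | mITT as written | Proposed rule |
|---|---|---|---|---|
| Before Day 42 | none scheduled | subject kept | subject deleted | subject kept, scores from onset blanked |
| Day 42 to Day 84 | Day 42 | kept | Day 42 lost | Day 42 kept |
| Taper | Day 42 and Day 84 | kept | both lost | both kept |

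A subject whose relapse needs no therapy can stay in the study and supply every score. Read literally, the mITT still removes that subject.

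**3. Share of relapsing subjects who lose valid scores.** Assume onsets spread evenly over Days 1 to 91, and ignore visit windows and other dropout. Onset after Day 42: (91 − 42)/91 = 49/91 = 54%. Onset in the taper: 7/91 = 8%.

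**4. Loss of numbers.** The plan is 510 subjects, 3 × 170 = 510. No relapse rate or power basis is available in the documents, so both are assumed. Take the standardised effect detectable with 80% power at 170 per arm, two-sided 0.05: (1.960 + 0.842) × √(2/170) = 0.304.

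| Assumed relapse per arm | Subjects left per arm | Power |
|---|---|---|
| 1% | 168 | 79.5% |
| 3% | 165 | 78.8% |
| 5% | 162 | 78.1% |
| 10% | 153 | 75.7% |

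**5. Selection.** Let r be the share removed from an arm and D the mean change in kept subjects minus that in removed subjects. Deletion moves the arm mean by r × D. The treatment contrast moves by r × D in the AERT arm minus r × D in the placebo arm. If D is 1 to 4 points in size (assumed), the shift in one arm runs from 0.01 × 1 = 0.01 to 0.05 × 4 = 0.20 at 1% to 5% relapse, and reaches 0.10 × 4 = 0.40 at 10%. TNmAS-MAL runs from 0 to 3 × 5 = 15. The contrast moves by nothing if r × D is equal in both arms. The documents give no basis for a direction.

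**6. The mWOCF analysis.** SAP 7.3.2.2 says "subjects who withdraw from the trial early due to an AE will have their missing data imputed using WOCF" and carries the last observation forward for the rest. SAP 7.3.3 assigns an early-termination score to the closest visit or, if that is filled, to the next one. So a subject with both a Day 42 score and an early-termination score has Day 84 filled, and a subject still missing Day 84 has at most one post-baseline score, for whom last and worst are the same. I enumerated early withdrawals on Days 2 to 83 with changes from −6 to +6. Day 84 was missing in 1,352 patterns. LOCF and WOCF differed in 0 of them using post-baseline scores only, and in 624 if baseline (change 0) counts as an observation. These are pattern counts, not expected frequencies.

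**The case against.** The strongest reply is that little depends on the mITT. It is a supporting population. Relapsing subjects stay in the primary ITT model and in the placebo-based pattern-mixture model, and those who discontinue stay in the penalised-score analysis. That is correct and limits the point to one supportive analysis.

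A second reply is that relapse in the mITT should be read by the protocol's only definition, treatment condition included. On that reading the untreated case disappears. The missing time window, the deletion of earlier scores and the selection after randomisation remain.

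A third is that the proposed rule will differ little from ITT, since most defined relapses already lead to withdrawal. This also stands, and is a cost of the fix.

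Two stronger readings are tempting, and the documents do not support them.

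- *Relapse withdrawals get LOCF and so escape the WOCF penalty.* No section says so. Protocol 12.4 lists Relapse and Adverse Event as separate withdrawal reasons, which suggests LOCF. But Protocol 9.7.2.1 counts as an AE "An exacerbation of a sign or symptom of an underlying condition", which suggests WOCF. The branch is undefined, and step 6 shows that it does not matter unless baseline counts. These subjects also stay in that analysis.
- *AERT intolerance will be labelled relapse and vanish.* AERT's expected AEs are in the Investigator's Brochure, which is not available here. The visible overlap is partial. Protocol 2.1 attributes to racemic baclofen the "side effects of sedation, drowsiness, and worsening of fatigue", and Protocol 9.2 monitors arbaclofen for orthostatic hypotension, with dizziness among its symptoms. Nothing found matches visual disturbance or tingling. The protocol's relapse definition also needs immediate therapy or a disease-modifying dose change, which drug fatigue alone would not meet.

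**Conclusion.** The point holds for the mITT analysis. As written, it removes whole subjects on an untimed post-randomisation event, discards scores that precede the event, and compares subsets that are no longer as randomised. This follows from the wording and does not depend on any assumed rate.

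The size cannot be fixed from the documents. Under the assumptions shown, 2 to 17 subjects per arm are lost (170 − 168 and 170 − 153), and power in this analysis falls by 0.5 to 4.3 percentage points from 80%. Exclusion of recent treated relapse (Protocol 5.2, criterion 3) may keep the rate low. Any shift in the contrast depends on relapse and outcome differing between arms, which the documents neither show nor rule out.

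The primary conclusion is not threatened. The mWOCF matter is a clarification only, with no numerical effect at Day 84 unless baseline counts as an observation.

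**What to change.** In Protocol 11.2 and SAP 7.1.3 and 9.1.3:

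- Keep every randomised subject in this supportive analysis.
- Set to missing only TNmAS-MAL and CGIC scores dated on or after onset of a relapse as defined in Protocol 12.4.
- Identify relapses and onset dates blind to treatment, and finalise the list before unblinding.
- Report the number and timing of relapses by arm. The separate mITT counts in SAP 8.1 and baseline table in SAP 8.3 then become redundant.

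As a clarification in SAP 7.3.2.2 and 9.1.3, state which mWOCF branch a relapse withdrawal takes and whether the worst observation may be the baseline. The abbreviation should also be expanded the same way in both places (modified in one, multiple in the other).

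The cost is a few sentences in two documents and a relapse onset date for each event. The analysis will differ little from ITT, and it relies on missing at random for the blanked scores. If a drug effect were wrongly labelled relapse, its later scores would still be blanked, so the by-arm report and the pattern-mixture model remain necessary. No rule on withdrawing or treating relapsing subjects changes.
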